Study logs: We will use study logs to examine the number of potential participants screened, consented, and reasons for declining consent. Study clinicians will document the amount of time that they spend during BUP induction using the microdosing or TAU protocol following a check-list of steps.

Ecological momentary assessment (EMA): We will use EMA to examine opioid and pain-related symptoms (opioid withdrawal and craving, pain, anxiety), along with illicit opioid use, BUP dose taken, and pain treatments. Using smartphone mobile technology, participants will receive time-scheduled prompts to report symptoms, ecological conditions (e.g., current activities), and behaviors. We will record assessments in two periods: the first 2 weeks (induction) and 3-month follow-up. During induction, participants will report opioid- and pain-related symptoms at random times during 5 daily blocks. The relatively long period of data collection oriented to induction will allow EMA data collection in the hospital and after participants return home to resume normal activities. During follow-up, we will collect data during three additional 1-week “bursts” to complement data from in-person study visits. Bursts will be separated by at least 2 weeks and no more than 6 weeks over 3 months. Prompts will inquire about opioid- and pain-related symptoms, and context, such as physical activity, which may affect these symptoms and OUD or pain outcomes. As with our current studies, research staff will assist in downloading the secure customized EMA technology (www.llumivu.com) onto participant smart phones, and provide training to use the technology.¹⁰⁶ Participants without smart phones will be provided one. Each report will take 1-2 minutes to complete. Based on the lack of significant reactivity effects found in past research, 5 standard EMA random reports will be prompted daily.^{117,118} EMA measures are summarized in **Table E-4**.

Adherence to EMA: Participants will receive \$0.20 for each set of assessments completed. If they complete more than 90% of assessments weekly, they will receive a bonus of \$10. Feedback regarding EMA adherence will be provided with reminders about compensation. Total compensation can be \$17 per EMA week.

E.2.10 Key Outcomes for Aims 1 and 2:

The **primary outcome** will be **BUP uptake**, defined as receiving BUP 7 days after the baseline visit using EHR data on hospital medication administration or prescription (dichotomous, yes/no).

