Secondary OUD outcomes include illicit opioid use and BUP retention. **Illicit opioid use** will be examined as the number of days of illicit opioid use (defined as self-reported use of heroin, fentanyl, or non-prescribed opioid analgesics) in the prior 30 days based on the Addiction Severity Index (continuous).¹¹⁹ Because urine drug testing (UDT) only captures opioid use in the prior 24-72 hours, it is a less sensitive measure of substance use over time; however, UDT results will be a secondary outcome measure. **BUP retention** will be

Table E-4. Ecological Momentary Assessment (EMA) Measures

Construct	Measure
EMA opioid- and pain-related symptoms	
Opioid withdrawal	Subjective Opioid Withdrawal Scale (SOWS)
Opioid craving	Visual analog scale
Pain intensity	Adapted BPI pain severity subscale
Anxiety	Generalized Anxiety Disorder-7 (GAD-7)
Exploratory EMA outcomes	
Illicit opioid use	Self-report
BUP dose	Self-report
Pain treatment	Self-report

*All measures will occur at bursts 1 & 2 weeks, and 1, 2, & 3 months

defined as having a BUP prescription written the following number of days after baseline: 30-60 days (1-month retention); 90-120 days (3-month retention); and 180-210 days (6-month retention). To be retained at 3 and 6-months, participants will be required to have been retained at previous time points.⁴⁶ All OUD outcomes are consistent with elements of the Opioid Use Disorder Cascade of Care.¹²⁰

Secondary pain outcomes include pain intensity, pain interference, and quality of life. *Pain intensity* will be measured using the Brief Pain Inventory (BPI).¹²¹ We will use the mean of 4 items that assess pain intensity over the past 24 hours on a scale of 1-10 (1=minimal pain, 10=intense pain). We will use the mean of these 4 items. *Pain interference* will be measured using the pain interference scale from the BPI, which is a 7-item instrument measuring the impact of pain on daily activities and physical functioning. It is rated on a scale of 1-10 (1=minimal interference, 10=high interference). We will use the mean of these 7 items. *Quality of life* will be measured using the PROMIS-Preference Scoring System (PROP-Pr), which is described in detail as part of the cost-effectiveness analyses below (see D.4.1).¹²²⁻¹²⁴ In our main analyses, we will examine changes from baseline to 3 months for all pain outcomes; in additional analyses, we will examine sustainability at 6 months.

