H₁: *The microdosing arm (vs. TAU) will have better BUP treatment uptake and retention, and less illicit opioid use.* Our primary analysis will be a logistic regression comparing the proportion of participants in each study arm who meet our definition of BUP uptake (see D.2.10). Secondary analyses will examine BUP retention and illicit opioid use as secondary outcomes. We will use a mixed effects logistic regression model to examine BUP retention at 1, 3, and 6 months and a mixed effects linear regression model to examine number of days of illicit opioid use (over 30 days) at 1, 3, and 6 months. Study arm will be considered a fixed effect, and participant and time (months) will be considered random effects. Additional analyses will include key variables mentioned above as covariates and potential confounders if they differ by study arm.

H₂: *Improvements in H₁ will be mediated by opioid- and pain-related symptoms.* Based on the model

described in **Figure E-3**, we will use structural equation modeling to determine whether improvements in OUD outcomes are due to improvements in opioid- and pain-related symptoms. We will use EMA data (5 random reports per day) and data from in-person visits at baseline, 1 week, 1, 3, and 6 months. For example, when the dependent variable is BUP uptake, we will calculate the standardized total effect from the intervention (BUP microdosing) to BUP uptake, as well as the standardized mediational (i.e., indirect) effect of opioid- and pain-related symptoms (e.g., withdrawal). The mediational effect is calculated as the product of the effect from intervention to the mediator, and the effect from the mediator to the outcome. To account for the influence of the baseline measures (e.g., sociodemographic characteristics) on the outcome and the mediator, we will use a partial correlation matrix as the input matrix. This will be created by statistically parsing out the effects of the baseline measures cited above on the mediator and the outcome variable. Our proposed model will be estimated using Mplus.¹³⁰ Overall model fit will be assessed by: (1) the root mean

[figure not shown]

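### H2 sets no time window for the symptom mediators of day-7 BUP uptake, so symptoms reported after the outcome are not kept out of the mediation model

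*Combined protocol and SAP*

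**What the plan says.** Section E.2.10 defines the primary outcome, BUP uptake, as "receiving BUP 7 days after the baseline visit using EHR data on hospital medication administration or prescription".

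Section D.2.11, H2, tests whether improvements in OUD outcomes run through symptoms. Its data are given in one sentence: "We will use EMA data (5 random reports per day) and data from in-person visits at baseline, 1 week, 1, 3, and 6 months". The worked example follows directly: "For example, when the dependent variable is BUP uptake, we will calculate the standardized total effect from the intervention". The estimator is a product of two paths: "The mediational effect is calculated as the product of the effect from intervention to the mediator" and the effect of the mediator on the outcome. H2 states no mediator window for any outcome. It refers to Figure E-3, which is not shown in the text available.

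Section D.2.9 on EMA says "We will record assessments in two periods: the first 2 weeks (induction) and 3-month follow-up" and that "5 standard EMA random reports will be prompted daily". The footnote to Table E-4 reads "All measures will occur at bursts 1 & 2 weeks, and 1, 2, & 3 months". Exploratory analysis E1 also treats induction as weeks 1 and 2. Section B.7 pairs symptoms with uptake in the induction period, and with the other OUD outcomes in follow-up.

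**The concern.** A product of paths has a causal reading only if the mediator comes before the outcome. The plan's own rationale (B.2) is that BUP prevents withdrawal and reduces craving. Participants on BUP at day 7 should therefore report fewer symptoms on days 8-14 because they are taking it. If more microdosing participants take it up, the arm lowers week-2 symptoms through uptake, and lower week-2 symptoms go with uptake. Both paths then point in the hypothesised direction even if symptoms had no influence on who took up BUP. Neither the robust standard errors nor the fit indices named for the model (RMSEA, CFI, SRMR) would reveal a reversed arrow.

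At stake is the proposed mechanism: H2 is where the trial would show that fewer symptoms during induction lead to more uptake. The team does fix time order elsewhere. E2 uses pain at one report to predict illicit use before the next, controlling for the previous pain level. H2 has no such rule.

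**Working it through.** **1. Prompts before and after the outcome.**
- Per week: 5 x 7 = 35. This reproduces the plan's maximum weekly EMA payment: 35 x $0.20 + $10 = $17.
- Induction: 5 x 14 = 70 prompts, of which 70 - 35 = 35 (50%) fall after day 7.
- All EMA: 5 weeks x 35 = 175 prompts, of which 175 - 35 = 140 (80%) fall after day 7.
- Visits: those at 1, 3 and 6 months come after the outcome, and the 1-week visit coincides with it. In Table E-3, in-person craving and GAD-7 have no 1-week entry, so their only post-baseline values come later than day 7.

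**2. Uptake inputs.** D.2.12 gives 61% (microdosing) vs 24% (TAU) and 27 per arm for 80% power. With an assumed two-sided alpha of 0.05 and pooled proportion 0.425:

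n = [1.96 x sqrt(2 x 0.425 x 0.575) + 0.842 x sqrt(0.61 x 0.39 + 0.24 x 0.76)]^2 / 0.37^2 = 26.8, so 27.

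The figure reproduces and is not in dispute. The planned size is 135 per arm.

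**3. How the false path arises.** Suppose symptoms do not affect uptake, and BUP lowers symptoms on days 8-14 by 0.5 to 1.0 unit (assumed).
- Arm difference in week-2 symptoms at 61% vs 24%: 0.37 x 0.5 = 0.185 to 0.37 x 1.0 = 0.37 unit. In a 14-day mean this halves to about 0.09 to 0.19.
- Within each arm, takers and non-takers differ in the 14-day mean by 0.25 to 0.5 unit.
- If the arm also lowers week-1 symptoms by up to 0.5 unit (assumed), up to 0.25 more is added to the arm difference in the 14-day mean.

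**4. Simulation.** 135 per arm; between-person SD 1, weekly noise SD 0.7; true indirect effect zero; relief 0.5-1.0 unit on days 8-14; arm effect 0-0.5 unit in week 1. False mediation means that both paths are significant.

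| Uptake | 14-day mean | Days 1-7 only |
|---|---|---|
| 44% (assumed) vs 61% | about 2-64% | about 0-5% |
| 24% vs 61% (D.2.12) | about 3-82% | about 0-3% |

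A more cautious set assumed no arm effect in week 1, correlation 0.5 between weeks and relief of 0.3-1.0 SD. The 14-day mean then gave 2-41% at 24% vs 61%, and 1-11% at an assumed 45% vs 61%. Days 1-7 gave at most 0.4%. The spurious share of the total effect with the 14-day mean was 1-7%.

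**5. What the day-7 cut does not do.** The low rates for days 1-7 depend on BUP leaving symptoms unchanged until day 7. Table E-2 starts BUP on day 1 (microdosing) or day 2 (standard induction). When BUP also lowered week-1 symptoms by 0.25-0.5 unit (assumed), false mediation with days 1-7 ranged over 2-89%, and over 1-91% in a repeat. In some scenarios it exceeded the 14-day mean (for example 88% against 64%).

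**The case against.** The strongest reply is that the data sentence is one pooled list for three kinds of outcome. Retention and illicit use at 1, 3 and 6 months need the later visits, and those visits also supply the outcome data. B.7 points away from follow-up data for uptake, E1 models induction and follow-up separately, and Figure E-3 may show the time order.

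Much of this stands. A reader might infer that the plan actually takes uptake mediators from week-2 EMA and from visits up to 6 months, and so counts relief produced by BUP as a cause of uptake. The documents do not say so: they leave it open. The case for the later visits is the weaker part. The two-week EMA part survives, because even the favourable reading in B.7 leads to an induction period that the plan defines as 14 days.

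Two further points stand. The outcome is receiving BUP on day 7, not starting it, so some symptom change within days 1-7 may already be due to BUP. And the 14-day mean and joint-significance test are simplifications: the plan specifies structural equation modelling with a robust estimator, and does not say how EMA reports are summarised.

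**Conclusion.** The concern holds as a gap in specification with a real consequence. H2 does not prevent symptoms reported after day 7 from entering as mediators of day-7 uptake, and half of the induction prompts fall there. If they enter, mediation can appear where none exists. The direction was the same in every set of runs, but the rate depends on assumptions that the documents do not supply: the size of BUP relief, the arm effect on week-1 symptoms, the correlation between weeks and, in some runs, a TAU uptake of 44% or 45%.

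It would be wrong to conclude that a window ending at day 7 makes the analysis clean. It reduces reverse causation and does not remove it. It would also be wrong to extend the point to the primary logistic regression or the sample size, neither of which uses these mediators. H2 is a mechanistic hypothesis, so this should be corrected before analysis but does not threaten the main result.

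**What to change.** State a mediator window for each H2 outcome.

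- **Uptake:** use only EMA and COWS/SOWS reports dated before the day-7 outcome assessment. Use the recorded dose times to separate symptoms before and after the first BUP dose, for example as a sensitivity analysis.
- **Retention:** use symptom data dated before each prescription window opens (days 30, 90 and 180).
- **Illicit use at 3 and 6 months:** use symptom data from before the 30-day look-back, that is, before about day 90 - 30 = 60 and day 180 - 30 = 150.
- **Illicit use at 1 month:** the look-back starts at about day 30 - 30 = 0, so only baseline data precede it, and these cannot mediate a randomised effect. Report this result as association rather than mediation.

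The cost is that about half of the induction EMA reports go unused in the uptake mediation model: 35 of 70, or 40 of 70 if day 7 itself is excluded (6 x 5 = 30 kept). A COWS score taken at the 1-week visit may also drop out if it is not dated before the outcome assessment. EMA reports are already time-stamped and administered doses already recorded, so no new data are needed.

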B.3 Fear of withdrawal prevents people from initiating BUP. Needing to transition to BUP from opioid agonists (i.e. heroin or prescription opioids) prevents people with opioid misuse or OUD from starting BUP. There are two challenges: 1) patients must typically avoid opioids for 24-72 hours before starting BUP; and 2) *precipitated or persistent withdrawal* during BUP induction can lead to early treatment cessation. If BUP is taken too soon after full opioid agonists, opioid-dependent people will experience precipitated withdrawal when BUP displaces other opioids at mu opioid receptors while providing only partial agonism. Relative reduction in opioid agonist activity is experienced as withdrawal,^{44,50,51} which can reduce interest in BUP treatment.^{52,53} People taking prescribed opioids express fear of stopping opioids due to worsening pain and withdrawal.^{9,10,54-57} Two early studies that attempted to transition patients with CP and likely OUD from prescription opioids to BUP highlight induction challenges. In one trial, 21 patients consented to transition from prescription opioids to BUP, but only 12 took BUP and 4 successfully completed induction.⁵⁸ In a retrospective pain clinic study, only 104 of 271 patients receiving prescription opioids who were offered BUP successfully transitioned to BUP.⁸ One study of 76 CP patients with opioid misuse used an inpatient protocol to transition to BUP; the protocol included conversion to intravenous opioids and giving small doses of intramuscular or sublingual BUP.⁵⁹ This worked, but elective hospitalization for BUP induction is too resource intensive to be generalizable. Even when BUP induction is successful, as many as 28% of patients drop-out during the first week of treatment, likely due to

Figure E-1. Study summary

uncontrolled craving and withdrawal.⁶⁰⁻⁶⁴ Improved BUP induction protocols are needed.

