D.2.1 Overview of study approach: We will conduct a hybrid type 1 effectiveness-implementation study, using a pragmatic, open label RCT. We will recruit 270 hospitalized patients with (a) CP and (b) opioid misuse or OUD, randomize them 1:1 to BUP microdosing or TAU, and link them to outpatient BUP treatment. We will assess BUP treatment uptake (primary outcome) and other OUD and pain outcomes. The microdosing arm will use a 5-day BUP microdosing protocol (see **Figure E-2** and **Table E-2**) – BUP doses will be gradually increased while a full opioid agonist is continued. In the TAU arm, participants will stop other opioids and wait until they are in moderate opioid withdrawal before starting BUP. Both arms will receive follow-up care at Montefiore clinics to continue BUP treatment (with buprenorphine-naloxone) and manage CP. Assessment visits will occur at baseline, 1 week, and 1, 3, and 6-months. We will use EMA to assess opioid- and pain-related symptoms during induction and three 1-week periods over 3 months. We will also collect detailed information on microdosing implementation and cost-effectiveness.

D.2.2 Setting. We briefly describe study sites below and details are provided in the Facilities section. Montefiore Medical Center is the largest healthcare provider in The Bronx. The neighborhoods served by Montefiore are representative of low-income urban areas: over 65% of patients have public insurance, 57% Hispanic and 39% Non-Hispanic Black, and neighborhoods have been devastated by drug use. There are three Montefiore hospitals in the Bronx. Hospitalized medical patients are typically cared for by hospitalists with the availability of pain, addiction medicine, and psychiatry consultants. Montefiore also has 20 community health centers, the BUP Treatment Network (situated in 7 community clinics), and 5 opioid treatment programs. In outpatient settings, patients receive BUP treatment integrated with primary care services.

D.2.3 Participant Eligibility: We will enroll hospitalized patients with CP and opioid misuse or OUD who are taking opioids and eligible for BUP treatment. Opioid misuse will be defined as heroin use or prescription opioid misuse (defined as: 1) use without a prescription; 2) use in greater amounts, or more often than prescribed 3) running out of prescription pain medication early).¹⁰⁷ CP will be defined as pain that is chronic

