3	Full dose	2 mg q8	6 mg	--	8 mg BID	16 mg
4	Full dose	4 mg q8	12 mg	--	8 mg BID	16 mg

D.2.7 Clinical Protocols: Microdosing**(Experimental arm):**

Participants randomized to microdosing will start low-dose BUP while continuing a full opioid agonist according to a 4-day protocol (see **Figure E-2 & Table E-2**). Participants will be assessed for opioid withdrawal using the clinical opioid withdrawal scale (COWS) before the first BUP dose and 30 minutes after each administered dose while hospitalized.¹¹¹ A full opioid agonist will be continued until day 5 of the protocol.^{112,113} If patients are planned for discharge before completing

microdosing, they will receive at the time of discharge pre-packed medication clearly marked with the timing for each dose, instructions on how to take the medication and when to stop full agonist opioids. Opioid withdrawal will be assessed with the Subjective Opioid Withdrawal Scale (SOWS) via telephone.

Rationale for 5-day protocol: Published microdosing protocols range from 3 to 7 days or more. From 2012-2016, the mean length of stay for patients at Montefiore Medical Center with an opioid positive urine drug test was 7.62 days (95% CI: 7.44-7.80). Some evidence suggests that rapid titration to maintenance BUP treatment dosages prevents drop-out,¹¹⁴ but rapid titration could increase precipitated withdrawal risk, therefore, we developed our protocol in the middle of the published range.

TAU (Control arm): Participants randomized to TAU will receive a standard BUP induction following clinical guidelines. Full opioid agonists will be stopped and a clinician will assess for withdrawal using the COWS scale. If participants have a COWS score of ≥ 8 they will be eligible to receive a 2 mg BUP dose. Participants will be reassessed for withdrawal 30 minutes after receiving their first BUP dose.

Withdrawal management: Participants with COWS score increases of $\geq 50\%$ or an absolute increase of 4 or more will be considered to have precipitated withdrawal. If this occurs, induction will be postponed to the following day. Clinicians can administer non-opioid adjunctive medications (i.e., clonidine, loperamide) during induction based on hospital protocols. Medication use will be considered a covariate in analyses with withdrawal symptoms as an outcome.

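### For withdrawal and buprenorphine uptake, the H2 mediation text assumes one common slope in both arms, although withdrawal is a gate to the first dose in TAU only; arm-specific indirect effects should be reported beside the pooled product

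*Combined protocol and SAP*

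**What the plan says.** D.2.11 tests H2 by structural equation modelling and defines the mediational effect as "calculated as the product of the effect from intervention to the mediator, and the effect from the mediator to the outcome". Its worked example has BUP uptake as the dependent variable and withdrawal as the illustrative symptom. Baseline measures are removed through a partial correlation matrix. The interactions that D.2.11 names are with sex, treatment by time (E1) and pain by BUP initiation (E2); none belongs to H2. The path diagram, Figure E-3, is not shown in the available text.

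The arms use withdrawal differently:

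- **TAU.** D.2.1: "In the TAU arm, participants will stop other opioids and wait until they are in moderate opioid withdrawal before starting BUP". D.2.7 says of TAU participants with a COWS score of at least 8 that "they will be eligible to receive a 2 mg BUP dose".
- **Microdosing.** D.2.1: "BUP doses will be gradually increased while a full opioid agonist is continued". No withdrawal threshold for starting is given.

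One rule is shared. When the COWS rise meets the definition of precipitated withdrawal, D.2.7 says "If this occurs, induction will be postponed to the following day". It names no arm.

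B.3 describes withdrawal as a deterrent, since precipitated or persistent withdrawal "during BUP induction can lead to early treatment cessation". D.1.3 adds that complicated inductions go with lower 30-day retention.

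**The concern.** A single product needs a single mediator-to-outcome slope. Under intention to treat, a TAU participant who never reaches withdrawal, for instance because other opioids were not stopped, contributes low withdrawal and no BUP. That pushes the TAU slope upwards. Withdrawal after dosing that makes someone give up pushes it downwards. Only the second mechanism is built into microdosing. The Specific Aims make a similar separation: avoiding the waiting period in withdrawal, and avoiding precipitated withdrawal. One pooled slope cannot tell these apart.

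At stake is the mechanism claim. H2 is a stated Aim 1 hypothesis and the momentary symptom data are the declared target of engagement. A small pooled product could be reported as no mediation when the arms merely differ.

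**Working it through.** **1. What the visible text can carry.** A correlation matrix of arm, mediator and outcome holds pairwise associations only. It cannot represent an arm-by-mediator effect unless a product variable is added or separate matrices are used by arm. The text mentions neither.

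**2. Inputs from D.2.12.** 135 per arm; uptake 61% and 24%. The plan gives no figure for H2, so its primary-outcome calculation was reproduced to confirm these inputs. Two-sided alpha of 0.05 is assumed because none is stated. With mean proportion 0.425:

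n = [1.96 × √(2 × 0.425 × 0.575) + 0.842 × √(0.61 × 0.39 + 0.24 × 0.76)]² / 0.37² = (1.370 + 0.546)² / 0.1369 = 26.8, so 27 per arm, as stated.

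**3. Assumed inputs, none in the documents.** Withdrawal has within-arm SD 1; microdosing lowers it by 0.5 SD (a = -0.5); log-odds slopes of uptake on withdrawal are varied by arm. Marginal uptake is held at 24% and 61%.

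**4. Method.** The pooled slope b comes from a linear model of uptake on arm and withdrawal with robust standard errors. The pooled indirect effect is a × b. It counts as detected when both paths are significant. It is compared with the natural indirect effect in each arm, on the risk-difference scale. Positive means that less withdrawal raises uptake. There were 2,000 simulated trials per row.

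| Slope TAU | Slope micro | Indirect, TAU | Indirect, micro | Pooled | Significant, positive | Significant, negative |
|---|---|---|---|---|---|---|
| -0.6 | -0.6 | +0.055 | +0.068 | +0.059 | 97% | 0% |
| 0 | -0.6 | 0.000 | +0.068 | +0.033 | 67% | 0% |
| +0.3 | -0.6 | -0.026 | +0.068 | +0.019 | 28% | 0.1% |
| +0.6 | -0.6 | -0.048 | +0.068 | +0.008 | 7% | 0.5% |
| +0.8 | -0.6 | -0.060 | +0.068 | 0.000 | 2% | 2% |
| +0.8 | -0.2 | -0.060 | +0.024 | -0.021 | 0% | 31% |

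**5. Why it behaves this way.** The pooled slope is roughly an average of the arm slopes, weighted by n times the variance of withdrawal in each arm. With equal variances the weights are one half each. Row 2: (0.000 + 0.068) / 2 = 0.034, against 0.033 simulated. Row 4: (-0.048 + 0.068) / 2 = 0.010, against 0.008.

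Unequal spread shifts the weights. If the microdosing SD is half that of TAU, they are 1 / (1 + 0.25) = 0.8 for TAU and 0.2 for microdosing. With a = -0.8 and slopes +0.6 and -0.6, the arm values are -0.084 and +0.115. The average is 0.8 × (-0.084) + 0.2 × 0.115 = -0.044; simulation gave -0.043, significantly negative in 38% of trials.

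**6. Price of arm-specific slopes.** Each uses 135 participants, not 270, so the standard error grows by about √(270 / 135) = 1.41; simulation gave roughly 40-45%. With equal slopes of -0.5 and assumed uptake of 30% and 60%, the pooled slope was significant in 97% of trials, the arm-specific slopes in 71% and 75%, and both together in 53%.

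**The case against.** A reader might infer that the two arms have opposite slopes and that H2 will therefore return a null or reversed result. The documents do not support that. A gate at the first dose does not show that more withdrawal means more uptake within TAU. B.3 and D.1.3 point to a negative component in standard induction as well, and no estimate of the TAU slope is given. If both slopes are negative but unequal, nothing cancels: with assumed slopes of -0.2 (TAU) and -0.5 (microdosing) and a 1-SD shift, the pooled slope was significant in 78% of trials. If the arm effects truly have opposite signs, no single sign is the correct one, so calling the pooled sign wrong is also loose.

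A reader might also treat the postponement rule as the microdosing counterpart of the TAU gate. It is not. The rule names no arm, TAU participants are reassessed 30 minutes after their first dose, and a one-day delay need not change receipt of BUP 7 days after baseline.

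Three limits on scope also stand. The gate uses clinician-rated COWS, whereas the momentary measure in Table E-4 is the self-reported SOWS, so the gate acts on the mediator only as far as the two scales agree. Figure E-3 might show an interaction that the text omits. The argument covers withdrawal and uptake; it has not been made for craving, pain, anxiety, retention or illicit use.

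These points remove certainty about direction and narrow the claim. They leave the common-slope assumption in the plan's own worked example, and the asymmetry of the first-dose gate, as they are.

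**Conclusion.** The point holds for one pathway, withdrawal to uptake. The visible H2 text assumes a common slope that the design puts in doubt, because withdrawal is a precondition for the first dose in TAU only. Exact cancellation is not needed for harm: a TAU slope of zero halves the pooled effect and takes detection from 97% to 67%. With a positive TAU slope the pooled value may fall to about zero or below. All slopes, the shift in withdrawal and its spread are assumptions, so these figures show what could happen and do not forecast it. If the slopes are equal, the planned product is sound. The primary comparison of uptake is unaffected. This is a worthwhile, inexpensive improvement to a mechanism analysis.

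**What to change.** For withdrawal as mediator and BUP uptake as outcome, the SAP should:

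1. Pre-specify an arm-by-withdrawal interaction, or a two-group model, in the structural equation model.
2. Report the natural indirect effect for each arm, with intervals, alongside the pooled product.
3. State that a null pooled product will not be read as absence of mediation unless the arm-specific paths agree.
4. Enter TAU withdrawal before the first BUP dose separately from withdrawal after it, and say how participants who never receive a first dose are handled, since they have no value after dosing.
5. State in words whether Figure E-3 includes an interaction.

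No new data are needed: administered doses are recorded and the momentary reports are time-stamped. The cost is SAP wording and precision. Arm-specific slopes carry roughly 40-45% larger standard errors when the slopes are equal, which is why the pooled product should be kept beside them and not dropped. The other mediators and outcomes under H2 can stay as planned.
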